Sisters Network Triangle North Carolina (SNTNC) is an affiliate chapter of Sisters Network, Inc., a national African American breast cancer survivorship organization. SNTNC was established in 2003. Prior to the COVID-19 pandemic, SNTNC held separate monthly meetings in both Raleigh and Durham, NC. Since the pandemic, SNTNC combined the Raleigh and Durham meetings into one monthly virtual Zoom meeting. In the past, SNTNC has participated in research projects about survivorship, barriers to care, and treatment adherence.

For African American women diagnosed with breast cancer, our long-term goals are to decrease cancer-specific, cardiovascular, and all-cause mortality. The objective of this proposal is to conduct formative research to determine if the format and materials of the TOPS program are feasible and acceptable to overweight and obese African American breast cancer survivors. This project seeks to address the health disparities of overweight and obesity and cardiovascular disease among African American breast cancer survivors and benefits from the following: 1) the existing infrastructure of the SNTNC, the Raleigh/Durham chapter of a national African American breast cancer survivorship organization; 2) the successful weight loss of participants in the TOPS program; and 3) [name] experience with studies of the TOPS program. The outcomes will be a) determination of the feasibility and acceptability of the TOPS program by women of SNTNC; b) recommendations the women of SNTNC have to modify the program to make it relevant to their experiences; and c) preliminary weight change data for sample size calculations for a future RCT of TOPS for weight change among this population.

This work will develop the evidence base for a scalable weight loss intervention among African American breast cancer survivors – a population with poor breast cancer and cardiovascular outcomes. If effective, these results have the potential to help increase both the survival and quality of life for this population.

Design & Procedures

Research design. Part of the study design will be the further development of study documents including TOPS programs, survey questions, and focus group scripts. The documents will not be used until full IRB approval is granted for the final drafts via amendments.

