This project will be a six-month single arm study that will use qualitative and quantitative methods to measure the feasibility and acceptability of the TOPS program among African American breast cancer survivors. Qualitative methods will collect data about participants' perceptions of the program and suggestions for modification to make it relevant to them and their experiences. We will conduct up to five focus groups and up to 10 in-depth interviews. Quantitative methods will measure recruitment, retention, and weight change.

Subjects. Overweight and obese African American breast cancer survivors in the Sisters Network Triangle North Carolina (SNTNC).

Inclusion criteria:

18 years old and over

Women diagnosed with breast cancer

BMI ≥ 25 kg/m2 after completion of primary therapy (surgery, radiation, adjuvant or neo-adjuvant chemotherapy)

Regular access to a computer and internet

Exclusion criteria:

Under 18 years old

Have not had a breast cancer diagnosis

Currently undergoing infusion chemo therapy treatment

Do not have access to a computer and the internet

BMI is less than 25 kg/m2

Women whose oncology providers do not agree with their participation in a weight loss program Participating in another weight loss program

If on insulin or sulfonylureas and provider does not agree to help manage their medications. They will need a signed provider permission form.

Study Setting. The study will be conducted via Zoom. Since the COVID-19 pandemic, SNTNC has met online. Approximately 50 to 60 women participate each month. Thus, the group is used to meeting in the virtual space. Duration. Subjects will join newly formed TOPS chapters for 6 months. Then, they will be asked to participate in focus groups to collect data about their perceptions of the TOPS program.

Recruitment and Screening. The study will enroll up to 50 women, who will be recruited through the Sisters Network Triangle North Carolina (SNTNC). [name], MSN, RN, is a Patient Navigator at the Duke Cancer Center. She is also the co-founder, past president, and current program manager for SNTNC and she is an enthusiastic proponent of this project. She will assist with the recruiting efforts.

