There is an additional opportunity for some participants to become a TOPS leader. This weight loss program requires peer leadership, which means one member of each group will be the leader. This involves reading the materials ahead of time and taking a training on TOPS leadership. Participants will receive an additional compensation for each training module completed to become a TOPS leaders.

Data collection. Focus groups and interviews. All individuals who enroll in the study will be invited to participate in 6 month focus groups and interviews, even if they did not remain in the program. Groups will be led by an experienced moderator and last for 60-90 minutes using open-ended questions to elicit the most information. Focus groups will have up to 6 participants and will be conducted via Zoom by the Behavioral Health and Survey Research (BHSR) Core, led by [name], MPH. We will conduct up to 10 individual interviews with those who are unable to participate in the focus groups. The interviews will include the same themes as the focus groups. Evidence suggests that data saturation can occur within 12 interactions, with primary themes arising as early as six. In this way, we will be able to discover factors associated with program continuation and withdrawal. Focus groups and interviews will be taped and transcribed. Both [name]'s and [name]'s previous experiences with SNTNC have established these as acceptable forms of assessment with this group. All interviews will be audio recorded (via Zoom) and transcribed. All of the patient information will be stored in a secure, shared Duke drive that only the study personnel will have access to. The focus groups will be recorded and stored securely on Duke's Zoom platform, participants will be provided with a password to enter the virtual meeting. Audio will be shared to Duke Box. Notes about the interview, transcripts, and audio will be stored in Duke Box and stored in study records for at least six years after the study is done. After six years, we will destroy the records, or we will remove all information identifying participants.

Survey: All individuals who enroll in the study will be invited to complete a brief survey about their experience at the 6 month interval.

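### Does the protocol promise more about withdrawal than an invitation to women who left can deliver?

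*Protocol*

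**What the plan says.** Under Data collection, the protocol invites all enrolled women to focus groups and interviews at six months, "even if they did not remain in the program". For the individual interviews it states: "We will conduct up to 10 individual interviews with those who are unable to participate in the focus groups". These cover the same themes as the groups. It then cites a general benchmark for qualitative work (main themes from about six interactions, saturation within 12) and concludes: "In this way, we will be able to discover factors associated with program continuation and withdrawal".

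The ceilings are in three places:
- Research design: "We will conduct up to five focus groups and up to 10 in-depth interviews".
- Data collection: "Focus groups will have up to 6 participants".
- Recruitment and Screening: "The study will enroll up to 50 women".

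A separate survey has no ceiling: "All individuals who enroll in the study will be invited to complete a brief survey about their experience at the 6 month interval". The instruments are not yet final. The Research design paragraph makes part of the study the "further development of study documents including TOPS programs, survey questions, and focus group scripts", with final drafts to be approved by amendment before use.

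**The concern.** The sentence about withdrawal carries no condition, yet the number of women who left and are heard depends wholly on who responds. There is no quota, no reserved place and no expected dropout rate. The interviews are assigned by inability to attend a group, not by having left. The saturation benchmark just before the sentence refers to interactions in general, not to interactions with women who left.

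Women who leave a program are also often harder to reach than those who stay. If few of them take part, a reason for leaving could be missing from the transcripts and be read as not existing. One of the outcomes listed in Background & Significance is a set of recommendations for modifying the program, and reasons for leaving bear on those. A future randomised trial could then inherit a program adapted mainly to the women who stayed.

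**Working it through.** The protocol attaches no sample size, dropout rate or acceptance rate to this sentence, so there is no figure of its own to reproduce. Three checks apply.

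**1. Do the places run out?** Inputs from the protocol: at most 5 groups of 6, at most 10 interviews, at most 50 women.

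- Places: 5 x 6 + 10 = 40.
- Acceptance needed to fill them: 40 / 50 = 80%.
- Interactions: 5 + 10 = 15 at most, so the cited benchmark of 12 fits under the ceiling for the sample as a whole.

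Now assume 50 enrolled, 20% or 30% leaving, 80% of the women who stay accepting, and 40% or 80% of those who left accepting. None of these rates is in the protocol.

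| Leave | Left | Acceptance among those who left | Heard, left | Heard, stayed | Total |
|---|---|---|---|---|---|
| 20% | 10 | 40% | 4 | 40 x 0.8 = 32 | 36 |
| 30% | 15 | 40% | 6 | 35 x 0.8 = 28 | 34 |
| 20% | 10 | 80% | 8 | 32 | 40 |
| 30% | 15 | 80% | 12 | 28 | 40 |

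The expected total never exceeds 40, so the ceiling does not explain any loss of women who left. In the first two rows they make up 4/36 = 11% and 6/34 = 18% of those heard, against 20% and 30% of those enrolled. That gap comes from assuming that they accept half as often as the others. It does not come from anything in the design.

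**2. Will any women who left be heard?** If w women left and each accepts independently with probability r, the chance of hearing none is (1 - r)^w. Over assumed dropout of 10%, 20%, 30% and 40% (w = 5, 10, 15, 20) and acceptance of 20%, 30%, 50% and 70%, there are 16 combinations:

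- Expected number heard: from 5 x 0.2 = 1 to 20 x 0.7 = 14.
- Chance of hearing none: 0.8^5 = 0.33 at worst (10% leave, 20% accept), 0.7^5 = 0.17 with 10% and 30%, and 0.8^10 = 0.11 with 20% and 20%.
- In the other 13 combinations it is below 0.04.

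The two worst cases are those in which only five women leave at all.

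**3. Which reasons might be missed?** A reason held by a share p of women who left goes unheard among n of them with probability (1 - p)^n.

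- p = 1 in 5: 0.8^4 = 0.41, 0.8^6 = 0.26, 0.8^8 = 0.17, 0.8^12 = 0.07.
- p = 1 in 2: 0.5^4 = 0.06 at the smallest n.

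So a less common reason can well be missed when four women are heard, while a common one is unlikely to be. The protocol sets no requirement that a reason held by one in five be captured. It says that factors can be discovered, and with 4 to 12 women heard some would be.

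**The case for a change.** The strongest case for the concern is that the number of women who left and are heard is uncontrolled, and that over a plausible range of assumptions it can be small. With 20% leaving and 50% of them accepting, the chance of hearing at least six is only 0.38. With 10% leaving it is zero, because only five women left. Six is the lower figure in the protocol's own benchmark, and that benchmark was not stated for this subgroup. A conditional sentence would therefore be more accurate, and it would cost almost nothing.

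Part of this stands. The benchmark does not establish saturation among women who left, and a more cautious verb would be defensible.

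The rest does not amount to a defect. The protocol does not claim saturation in that subgroup, a complete list of reasons, or a comparison of women who stayed with women who left. Nothing in it treats an unmentioned reason as absent. The recommendations it seeks come from all participants, not only from those who left. Reporting participation by withdrawal status is ordinary reporting, and retention is already to be measured. A question on why a woman stopped belongs in a survey that is still being written, so its absence from the protocol shows nothing. Giving women who left priority for interviews would matter only if more than 40 women accepted.

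**Conclusion.** The concern does not hold. The sentence states a capability, and the design supports it by inviting women who left, offering an interview to those who cannot attend a group, and surveying everyone enrolled. The 40 places would bind only above 80% acceptance. With 20% to 30% leaving and 40% to 80% of them accepting, 4 to 12 would be heard. The chance of missing a reason held by one in five then runs from 41% down to 7%.

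Those figures rest on full enrolment of 50, on dropout and acceptance rates that the protocol does not give, and on a one-in-five criterion that it does not set. They describe the normal limits of voluntary, exploratory interviews and contradict nothing the protocol says. Participation cannot be compelled, so no wording or allocation of places could guarantee a number of women who left. Softening one verb is an editorial choice and would change no procedure or result.

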Purpose of the Study

Aim 1: Examine the feasibility and acceptability of a national, low-cost, community-based, peer-led, weight loss program (Take Off Pounds Sensibly, TOPS) for overweight and obese African American breast cancer survivors in the local chapter of a national African American breast cancer support group (Sisters Network Triangle North Carolina, SNTNC).

Hypothesis 1: The TOPS format, materials, and content will be feasible and acceptable to overweight and obese African American breast cancer survivors in SNTNC.

Aim 2: Assess the weight change of overweight and obese African American breast cancer survivors after 6 months in the TOPS program to gather data for sample size calculations for a future RCT.

Hypothesis 2: Overweight and obese African American breast cancer survivors in TOPS will lose 5% of their initial body weight, which is clinically significant, within 6 months.

Background & Significance

Mounting evidence links overweight and obesity to cancer. In women diagnosed with breast cancer, obesity contributes to both breast cancer-specific and cardiovascular disease mortality. In one study, breast cancer survivors diagnosed at ≥66 years were more likely to die from cardiovascular disease than breast cancer. Therefore, obesity also plays a role in their cardiovascular mortality. Unfortunately, breast cancer treatment can exacerbate these issues because it may be associated with weight gain; increased cardiovascular events; and decreased physical function.

Compared to the general population, African American women have higher rates of overweight and obesity among those with and without breast cancer; gain more weight after they are diagnosed with breast cancer; and have worse outcomes for breast cancer mortality and cardiovascular disease. For women diagnosed with breast cancer, interventions targeting diet, weight loss, and physical activity have been associated with clinically significant weight loss; decreased mortality; reduced risk of breast cancer recurrence; and fewer cardiovascular events. Unfortunately, African American women lose less weight than other groups in standard weight loss programs.

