In one randomized controlled trial, African American breast cancer survivors in an expert-led intervention – weekly didactic sessions, twice weekly supervised exercise sessions, and twice weekly text messages with community-based nutritionists and exercise trainers – lost an average of 3.6% of their weight and 44% of participants lost at least 5% of their initial weight. However, personnel increase the intervention costs, and there is no infrastructure for nationwide dissemination of this program. To decrease adverse clinical and mortality outcomes among African American breast cancer survivors, a weight management intervention with scalable infrastructure that can be implemented in low-resource settings is needed.

A national, low-cost, community-based, peer-led weight loss program (Take Off Pounds Sensibly, TOPS) can fill this unmet need. TOPS is a nonprofit, evidence-based weight loss program with a national infrastructure that offers a pragmatic option to help women diagnosed with breast cancer manage their weight. First, it includes all of the components that the NIH asserts should be included in "safe and effective" weight loss programs. Second, [name] retrospective analyses showed: 1) TOPS participants lose a clinically significant amount of weight and maintain the loss for up to 7 years. Third, its peer-led, community-based structure ensures each chapter is contextually tailored for its members. For instance, in a successful pilot study, [name] started three TOPS chapters specifically for older African American women; and one chapter continued for almost 8 years after the study ended in 2012 (until the COVID-19 pandemic). Fourth, TOPS costs participants less than \$100 per year. Finally, TOPS's nationwide infrastructure, with chapters in every state, can facilitate dissemination and implementation. However, because women with breast cancer have greater psychosocial stressors, including time-consuming treatment regimens and fear of recurrence, they may need different levels of support than those offered in standard TOPS chapters, and this study can reveal those elements and provide preliminary data for a future randomized controlled trial (RCT).

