[name] will attend up to two of the monthly SNTNC meetings, and she and [name] will present an information session about the study via a Zoom meeting. Individuals will be invited to contact the study team to determine if they are either overweight or obese based on self-reported height and weight and calculated BMI. If women qualify based on BMI, they will be asked pre-screening questions in REDCap to determine if they are eligible to participate in the study. Based on [name] extensive experience recruiting participants for previous studies, we believe we will be able to complete the recruitment phase within two months.

Participants that complete the screening questions and note that they are on insulin (such as, U-100, U-200, U-300, ultra long acting, pre-mix (i.e. 70/30, 75/25), U-500 (ultraconcentrated), inhaled insulin) or sulfonylureas (such as, glyburide [DiaBeta, Glynase, PresTab, Micronase], glipizide [Glipizide XL, Glucotrol, Glucotrol XL], glimepiride [Amaryl], tolazamide [Tolinase], or tolbutamide [Orinase]) they will need to get a permission form signed by their provider. The form will be sent via email to the participant to take to their provider. The permission form will be used to notify the patients provider that they would like to participate in a weight loss study which may cause changes to their diabetes medications. The PI will not be responsible for managing their medications so the participants' provider must sign the form stating that they will agree to help manage the participants medications if needed. If the participant does not get a signed permission form or their provider does not agree to help manage their medications they will be ineligible to continue with the study. The forms will be collected, uploaded, and noted in REDCap.

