Participants that attend the Zoom information session and are interested in participating in the study will be sent a link to our REDCap project. They will be able to review information about the study such as why we are doing the study, risks/benefits, and determine if they would like to continue by answering some questions. They will provide some information to identify themselves and to determine eligibility. Once eligible, participants will be able to review the e-consent. They can have as much time as needed to review, ask the study team questions via phone or email, and sign using an e-signature. After they sign they will be sent a copy of the e-consent via email that they provide. If they are ineligible, they will not be able to continue on to the e-consent.

Intervention. Participants will be invited to join new chapters of the TOPS weight loss program created for the study. Each participant will be offered a free one-year membership in the TOPS program. Participants will receive the "TOPS Plus" new member packet—one-year membership in a local TOPS chapter; My Day One: A Ready-Set-Go Guide for Healthy Living is a 24-page booklet of weight loss basics with a six-week lesson plan; a one year subscription to TOPS News, a bimonthly magazine published exclusively for TOPS members; Real Life: The Hands-on, Pounds-off Guide is a 304-page weight management lifestyle guide; Food Exchange Cards; TheraBands® Resistance Bands; My Real Progress, a 12-week food and fitness journal. TOPS Usual Procedures. The TOPS program usually consists of weekly private weigh-ins on the chapter scale, where the weight recorder notes each person's weight on their individual Weight Chart. Then, there is a group meeting, where members receive educational information on topics such as healthy eating, exercise, or behavior modification. Participants usually get a "provider-approved" weight goal. Modified COVID-19 Procedures. Because of social distancing requirements due to the pandemic, we will have to modify the usual procedures. The study will provide each participant with a scale, and members will provide the weight recorder with their weights each

week. The weight recorder will still record each person's weight on their individual Weight Chart. We will also set an initial weight loss goal of 5% of initial weight, which is considered clinically significant.

Additional Opportunity:

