Focus group and interview guide development. Focus group and interview guides will be developed using the Framework for Reporting Adaptations and Modifications – Enhanced (FRAME), which is typically used to retrospectively document modifications that occurred during implementation. In this case, we will use FRAME to guide questions for prospective adaptations for our population of interest. Instead of asking, "What is the nature of content modifications?" we will offer options for possible modifications, such as removing, substituting, or adding elements. Focus groups and interviews will inform the adaptation and implementation of the TOPS program for African American breast cancer survivors. Weight change. Weight change will be calculated at 3 and 6 months as percentage change from initial weight. If the pandemic restrictions allow and participants are comfortable, we can consider study visits for data collection. However, we plan to provide participants with smart scales to transmit data to a secure application.

Risk/Benefit Assessment

There is minimal risk to the subjects. Weight loss has been shown to be safe in obese, older individuals. Additionally, this study will recruit participants into Take Off Pounds Sensibly (TOPS), a nationally available, community-based, peer-led weight loss program. The TOPS program is being used in non-medical settings throughout the United States and Canada and poses minimal risk to participants. Individuals must have a body mass index of 25 or greater to participate in the current study. The minimal risk to human subjects for participation in this study is greatly outweighed by potential health benefits that may accrue participants and by the importance of the scientific knowledge that may reasonable be expected to result from this work.

Data Analysis & Statistical Considerations

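### Does the weight outcome mix measurement sources, with a self-reported baseline, badly enough to distort percent change?

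*Protocol*

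**What the plan says.** Weight appears in four places in the protocol, with different purposes.

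- **Recruitment and Screening.** Women contact the study team to "determine if they are either overweight or obese based on self-reported height and weight and calculated BMI". The stated use is eligibility.
- **Intervention, Modified COVID-19 Procedures.** The study gives each woman a scale, and "members will provide the weight recorder with their weights each" week. The recorder enters the weights on an individual chart. The same paragraph sets a first goal of 5% of initial weight.
- **Data collection, Weight change.** "Weight change will be calculated at 3 and 6 months as percentage change from initial weight". Two sentences on the source follow: "If the pandemic restrictions allow and participants are comfortable, we can consider study visits for data collection", and then, introduced by *However*, "we plan to provide participants with smart scales to transmit data to a secure application".
- **Data Analysis & Statistical Considerations, Weight change.** Change is computed by last observation carried forward and in completers, from baseline and as a percentage of initial weight. It is also grouped as gain, loss below 5%, and loss of 5% or more.

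Neither *baseline* nor *initial* weight is given a source or date, and no sentence requires the same source at every time point. Hypothesis 2 is that participants "will lose 5% of their initial body weight, which is clinically significant, within 6 months". The weight data are also meant to inform the sample size of a future randomised trial.

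**The concern.** A change score carries any systematic difference between the methods used for its two weights. Here the only weight expressly placed before the programme is the self-report at screening, while later weights could come from a home scale, the recorder's chart or a clinic visit. Whether a woman had a visit would depend on her comfort and on the calendar. On a literal reading, percent change could compare a self-reported weight with a scale weight, or a home scale with a clinic scale.

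The design makes this worth checking. There is one arm, so no control group absorbs such a difference. The outcome is also cut at 5%, so a modest shift moves women across the line. At stake would be the mean change and the share reaching 5%, the two summaries most relevant to Hypothesis 2 and to the future trial.

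**Working it through.** **Inputs.** From the protocol: the 5% target (Purpose of the Study); a comparator programme in which women "lost an average of 3.6% of their weight and 44% of participants lost at least 5% of their initial weight" (Background & Significance); enrolment of up to 50 women. The protocol gives no standard deviation (SD), body weight or measurement-error figure, so there is no stated figure to reproduce. Assumed: body weight W of 70, 90 or 110 kg, and a difference between methods of 0.5 to 2 kg. The true loss L is 5%.

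**1. Same issued scale throughout, constant offset o.** Observed loss = 100 × [1 − (W(1 − L) + o)/(W + o)].
- W = 90, o = +2: 1 − 87.5/92 = 4.89%. With o = −2: 1 − 83.5/88 = 5.11%.
- Widest case, W = 70: 1 − 68.5/72 = 4.86%, and 1 − 64.5/68 = 5.15%.

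The offset almost cancels.

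**2. Self-reported baseline under-reported by b kg, scale at follow-up.** Observed loss = 100 × [1 − W(1 − L)/(W − b)]. At W = 90:
- b = 0.5: 1 − 85.5/89.5 = 4.47%
- b = 1: 1 − 85.5/89 = 3.93%
- b = 2: 1 − 85.5/88 = 2.84%

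**3. Home scale at baseline, visit weight at follow-up reading o kg higher.** Observed loss = 100 × [1 − (W(1 − L) + o)/W]. At W = 90:
- o = 0.5: 1 − 86/90 = 4.44%
- o = 2: 1 − 87.5/90 = 2.78%

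Expressed simply, 0.5/90 = 0.6 points and 2/90 = 2.2 points, or 11% to 44% of the 5-point target. The two mechanisms with an evident direction, under-reporting at screening and clothing at a visit, both understate the loss.

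**4. Share losing at least 5%, normal model with mean 3.6%.** With an assumed SD of 6, the share is 41%. A downward shift of 1.1 points gives 34%, and 2.2 points gives 27%. The comparator's own figures imply a larger SD under this model: (5 − 3.6)/0.151 = 9.3. With that SD, 44% falls to 39% and 35% for the same shifts. The larger shift then costs 9 percentage points (44 − 35), against about 13 with SD 6 (40.8 − 27.4).

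**5. Cohort-level size.** Step 4 gives every woman the full shift. If only a fraction f changes method, the mean moves by f × shift. For illustration, f = one half turns 2.2 points into 1.1. For comparison, sampling error alone with 50 women gives a 95% half-width of 1.96 × 6/√50 = 1.7 points at SD 6, or 2.6 at SD 9.3.

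**6. Which case does the text describe?** Step 2 needs the screening weight to be the baseline, and no sentence makes it so. Step 3 needs visits to be adopted and their weights mixed with home weights, whereas the text only says visits can be considered. Step 1 fits the stated plan. The goal of 5% of initial weight appears in the paragraph that issues the scale and describes weekly recording, so the first reading on that scale is the natural initial weight. The scale in that paragraph and the later smart scale are plausibly one device. This is an inference, but on it the recorder's weights and the transmitted weights differ in reporting route, not in instrument.

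**The case for a change.** The strongest case for a change is that this is a matter of data collection, not analysis. An analysis plan can choose among weights already collected, but it cannot create a weighing before the programme that the protocol never schedules, and a missed baseline cannot be recovered. Carrying the last observation forward also opens a route to mixing: a woman who drops out may contribute a reported weekly weight while a completer contributes a transmitted or visit weight. Naming one source would be cheap and, as step 1 shows, would nearly remove the error.

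Part of this stands. The source and date of initial weight are not stated, one method is not required throughout, and the visit clause is open-ended. If methods were mixed within a woman, the error could be a material part of 5%.

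The rest is weaker. Weekly weighing on an issued scale makes an early scale reading available without a new procedure. Visit weights, if any are taken, can be kept apart at analysis. Mixing through carried-forward values matters little if the recorded and transmitted weights come from the same device. A strict rule admitting transmitted weights only also has a price: in a study of at most 50 women, each failed transmission becomes a missing value, and carrying forward would replace a usable chart reading with an older one.

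**Conclusion.** No change to the plan is called for. The protocol leaves a term undefined and mentions an option it has not adopted, but no stated rule produces a wrong result. On the natural reading, with the first and later weights from the issued scale, a constant offset of up to 2 kg moves a true 5% loss by no more than 0.15 points. The shift of 0.6 to 2.2 points arises only in women whose method changes between weighings. It rests on an assumed 90 kg body weight and an assumed 0.5 to 2 kg difference, neither of which the protocol supplies. It approaches half of the 5% target only at the upper end of that range.

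This conclusion depends on two readings that the text supports but does not state: that the issued scale supplies the initial weight, and that the chart and transmitted weights come from one device. Only the protocol is at hand, and which recorded weight serves as baseline is a detail commonly settled in an analysis plan or manual. Weight change is the second aim of a single-arm feasibility study, which further limits what is at stake.
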